7. Note that not all subjects will receive study drug at randomization. Refer to Section 8.5 and Figure 1 for more information.

Study arms 4 and 5: Subjects assigned to study arms 4 and 5 will receive both the study drug and vaccine on day 1. The study drug will be administered first, followed by the vaccine. There must be a minimum of 2 hours waiting period between administration of the study drug and subsequent vaccine administration. Approximately 24 hours after completion of the study drug and vaccine administration on day 1, subjects will be followed up by telephone for safety. Subjects should be monitored for at least 1 hour after study drug or vaccine administration.

Study arms 6a, 6b, 6c, and 6d only: Subjects assigned to one of these study arms will not receive study drug. These subjects will receive the vaccine only. These subjects should be monitored for at least 30 minutes after vaccine administration.

Refer to Section 9.2.2 for additional information concerning administration and monitoring requirements following study drug and/or vaccine administration.

8. Serology characterization assays will be used to assess antibodies against various SARS-CoV-2 antigens including: S protein, RBD, S1, and N protein. Refer to Section 9.2.3.1, Section 9.2.3.2, and Section 9.2.3.3 for more information on procedures and assays related to vaccine response assessment.
9. Vital signs, including temperature, blood pressure, heart rate, and respiratory rate will be collected prior to and 30 minutes following each administration of the study drug or vaccine primary series (first and second dose) as described in Section 9.2.4.1.
10. Actual dosing time and drug concentration sample collection times will be recorded.

Study arms 1, 2, 3, 7, 8, and 9 (receiving IV infusion of study drug): At the indicated visit, blood for assessment of drug concentration in serum will be taken prior to dosing and within 60 minutes after the end of infusion (EOI). The EOI sample should be collected from the arm contralateral to that used for IV infusion. If not medically feasible, the EOI sample can be drawn from the same arm, but not from the infusion catheter.

Study arms 4 and 5 (receiving SC injection of study drug): At the screening/baseline visit, blood for assessment of drug concentration in serum will be taken prior to dosing. The post-dose blood collection should occur at least 1 hour after study drug administration.

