9.2.3.2. SARS-CoV-2 Serology Characterization Assays

Serum binding antibodies to SARS-CoV-2 S protein trimer, RBD and other SARS-CoV-2 subdomains (including S1 and nucleocapsid) will be assessed as secondary and exploratory objectives of this study. To explore whether or not mRNA-1273 vaccine-mediated humoral immunity to SARS-CoV-2 is affected by the administration of REGN10933+REGN10987, serological immunoassays will be used to detect antibodies against the SARS-CoV-2 S protein and subdomains at time points in the Schedules of Events. Because REGN10933+REGN10987 will interfere with these measurements, an anti-idiotype antibody that blocks REGN10933+REGN10987 will be included in the assay, allowing for detection of endogenous serum antibodies generated *in vivo* post-vaccination. Additional serological characterization related to antibody recognition of viral variants and further delineation of the epitope repertoire of vaccine-induced antibodies may be done if technically feasible and assays become available.

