11.3. Analysis Sets

11.3.1. Vaccine Response Analysis Sets

The **modified full analysis set (mFAS)** includes all randomized subjects who have been vaccinated with at least one dose and have a negative serology test result from the central laboratory test at baseline; it is based on the treatment received (as treated).

The **per protocol set (PPS)** includes all randomized subjects who have been vaccinated with at least one dose and do not meet the PPS exclusion criteria; it is based on the treatment received (as treated).

The PPS excludes subjects who:

- Receive positive SARS-CoV-2 serology result based on central laboratory test at baseline
- Do not receive the second dose of the vaccine
- Receive a positive diagnostic test result for SARS-CoV-2 infection before 56 days after the first dose of the vaccine
- Receive any dose of a coronavirus vaccine (refer to Section 8.8.1) outside of the study within 56 days after the first dose of the vaccine
- Receive systemic immunosuppressants or immune-modifying drugs within 56 days after the first dose of the vaccine
- Receive IVIG or blood products within 56 days after the first dose of the vaccine

The SAP will document the finalized exclusion criteria for the PPS.

The PPS is the primary analysis set for assessing vaccine response.

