3.1. Per Protocol Set Analysis Set (PPS)

The per protocol set (PPS) includes all randomized subjects who have received both doses of vaccine and who do not meet the following exclusion criteria:

1. Have a positive SARS-CoV-2 central serology result prior to the first dose of vaccine.
2. Receive a positive Reverse Transcription Polymerase Chain Reaction (RT-PCR) diagnostic test result for SARS-CoV-2 infection at any time point prior to the scheduled visit 56 days after the first dose of vaccine.
3. Receive any dose of investigational or approved passive antibodies for SARS-CoV-2 infection prophylaxis (eg, convalescent plasma or sera, mAbs, hyperimmune globulin) outside of the study at any time point prior to the scheduled visit 56 days after the first dose of vaccine.
4. Receive any other vaccine within 28 days prior to the study to the scheduled visit 56 days after the first dose of Moderna mRNA-1273 vaccine administered as part of this study.

Exception: seasonal influenza vaccine is only prohibited within 14 days before or after study drug administration, or within 14 days before or after Moderna mRNA-1273 vaccine administration.

5. Receive systemic medications that suppresses the immune system (for corticosteroids, ≥ 20 mg/day of prednisone equivalent) at any time point prior to the scheduled visit 56 days after the first dose of vaccine.
6. Receive IVIG or blood products at any time point prior to the scheduled visit 56 days after the first dose of vaccine.
7. Subjects with incomplete infusions or injections of study drug or vaccine at any time point prior to the scheduled visit 56 days after the first dose of vaccine.
8. Subjects with baseline neutralization antibody titer above the lower limit of quantification (LLOQ).

The PPS is the primary analysis set for assessing vaccine response related endpoints.

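### After baseline, the SAP's per-protocol set removes infections on RT-PCR alone, although planned N-protein serology from the same visits could flag some that the swabs miss

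*SAP*

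**What the plan says.** **PPS rules in the SAP.** SAP 3.1 makes the PPS the primary set for vaccine response. Criterion 2 excludes subjects who "Receive a positive Reverse Transcription Polymerase Chain Reaction (RT-PCR) diagnostic test result for SARS-CoV-2 infection" before the visit 56 days after the first dose. Two other criteria rest on antibodies, but both look only at samples from before vaccination. Criterion 1 excludes those who "Have a positive SARS-CoV-2 central serology result prior to the first dose of vaccine", and criterion 8 excludes those with a quantifiable baseline neutralizing titre.

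**Wider rules elsewhere.** Protocol 11.3.1 excludes subjects who "Receive a positive diagnostic test result for SARS-CoV-2 infection before 56 days after the first dose of the vaccine", without naming a test type, and leaves the final criteria to the SAP. SAP 1.2.5 describes its change to the PPS only as added detail. The booster set in SAP 3.5 starts from the PPS and also excludes COVID-19 adverse-event terms, including asymptomatic infection and a positive test.

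**What is collected.** Protocol Tables 3 to 5 mark both the RT-PCR swab and the serology-characterization serum at the post-baseline visits. Footnote 8 in Protocol 9.1.1 states: "Serology characterization assays will be used to assess antibodies against various SARS-CoV-2 antigens including: S protein, RBD, S1, and N protein". Protocol 9.2.3.2 also names nucleocapsid. The binding-antibody variables in SAP 4.5.2 cover S, RBD, S1, S2 and NTD. N appears in no SAP variable and in no analysis-set rule.

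**The concern.** The trial asks whether the study drug lowers the titre that the vaccine induces. An infection between the first dose and day 56 can raise the titre for an unrelated reason. The plan recognizes this: SAP 1.1 says that exposure to the virus would confound interpretation, and criterion 2 is there to remove it.

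A swab can only find virus present on the day it is taken. Up to the primary visit the swabs fall on study days 15, 29, 43, 57 and 71 in waves 1 and 3, and at similar spacing in the other waves. A short or silent infection between visits can therefore leave no positive RT-PCR. The protocol treats mRNA-1273 as an S-based vaccine and both antibodies as directed at the RBD of S, so new anti-N antibodies point to infection and not to either study product.

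If missed infections are more frequent per subject in controls than in a drug arm, the control mean is pushed up and the drug arm looks too low. All eight drug arms are compared with one pooled control group (SAP 5.7.1), so a raised control mean enters every comparison. After day 56, visits are 84 to 113 days apart and the PPS infection rule has ended, yet SAP 8 says long-term vaccine response will be reported.

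**Working it through.** **Inputs from the documents**
- SD 0.30 log10; 30 subjects per drug arm and 46 pooled controls; stated half-width 0.14 (Protocol 11.2, SAP 2.2).
- A 66.4% reduction in overall infection with 1200 mg SC in a separate household-contact trial (Protocol 3.3.1), so the rate ratio RR = 1 − 0.664 = 0.336.

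**Assumptions, not in the documents**
- f: the share of PPS controls with a missed infection.
- d: the log10 titre rise from infection. A 5-fold rise gives 0.699 and a 10-fold rise gives 1.0.
- RR applies to missed infections as it does to all infections.

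**1. The plan's figure.** Half-width = 1.96 × 0.30 × √(1/30 + 1/46) = 0.138; with a t quantile on 74 df it is 0.140. The stated 0.14 is reproduced.

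**2. Net bias for one drug arm against controls.** Bias = f × (1 − RR) × d. With three missed infections, f = 3/46 = 0.065:
- d = 0.699: 0.065 × 0.664 × 0.699 = 0.030 log10, a geometric mean ratio about 6.7% too low.
- d = 1.0: 0.065 × 0.664 × 1.0 = 0.043 log10, about 9.5% too low.

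This is 22% to 31% of the 0.14 half-width.

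**3. Range over f, with d from 0.3 to 1.0 and RR 0.336**

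| f | Bias (log10) | Ratio too low by |
|---|---|---|
| 1% | 0.002–0.007 | 0.5–1.5% |
| 5% | 0.010–0.033 | 2.3–7.4% |
| 10% | 0.020–0.066 | 4.5–14.2% |
| 15% | 0.030–0.100 | 6.6–20.5% |

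**4. Dependence on RR, three missed infections in controls.** With RR = 1 (no protection) the bias is zero. With RR = 0 (no missed infection in the drug arm) it is 3/46 × d = 0.046 to 0.065, which is a ceiling.

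**5. Share needed to reach the half-width.** f = 0.138 / (0.664 × d), which is 21% of controls for a 10-fold rise and 30% for a 5-fold rise.

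**6. Where missed infections would lie by count**
- All 240 drug-arm subjects at RR 0.336: 46 / (46 + 240 × 0.336) = 36% in controls.
- Arms 2, 3, 7 and 8 (120 subjects) unprotected, the other 120 at RR 0.336: 46 / (46 + 120 × 0.336 + 120) = 22%.

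**7. The concurrent-control check in SAP 5.7.5.** Waves 3 and 4 have 8 + 8 = 16 controls. One missed infection shifts their mean by d/16 = 0.044 to 0.063. For arm 9 the net bias at RR 0.336 is 0.029 to 0.042, against a half-width of 1.96 × 0.30 × √(1/30 + 1/16) = 0.18.

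**The case against.** The strongest reply is that the effect is small and the plan already has safeguards. Subjects must report symptoms and outside positive results, and Protocol 6.1.2 then calls for a prompt RT-PCR, unscheduled if need be. Pre-vaccination serology and neutralizing titre are screened. The study is descriptive, SAP 2.2 uses 1.44 log10 as a benchmark, and the protocol lets the SAP settle the PPS criteria. Capping at the ULOQ (SAP 6.2) could also limit how far a boosted titre moves the mean. All of this stands and bears on size. None of it reaches a silent infection between visits.

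A second reply also stands: anti-N is not a perfect marker. The documents give no cut-off or sensitivity, and Protocol 9.2.3 says some of these analyses may not appear in the study report. An infection shortly before day 56 may not have seroconverted. The drug lowered viral load in treated outpatients (Protocol 3.3.1), so anti-N sensitivity could differ by arm, and excluding on it could introduce some selection. That last step is an inference, but it is a reason to prespecify an analysis both ways.

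A reader might infer that missed infections concentrate in the controls. The documents do not support that. Controls are 46 of 286 subjects and would hold about 22% to 36% of missed infections under the two scenarios in step 6. The 66.4% comes from one dose and route in another trial. It cannot be carried to the 12 mg and 48 mg IV arms, chosen to leave low concentrations at vaccination. All subjects here are also vaccinated, and arm 9 receives the drug only on day 7.

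**Conclusion.** The gap is real and minor. The primary analysis set relies on RT-PCR alone for post-baseline infection, while an N-protein result planned on serum from the same visits goes unused. The SAP rule is also narrower than the protocol's wording and the SAP's own booster set.

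The supported statement on direction is limited: a higher missed-infection rate per subject in controls than in the 1200 mg arms is plausible, and it would slightly overstate interference there. Against an unprotected low-dose arm the expected net bias is about zero.

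For three missed infections in 46 controls the net bias is about 0.030 to 0.043 log10, against 0.14. This rests on an assumed 5- to 10-fold rise, an assumed count, and a rate ratio borrowed from another trial. The larger 0.046 to 0.065 would require no missed infections at all in the drug arm, which the 66.4% figure does not imply. The day-56 conclusion is unlikely to change on this account alone. The long-term summaries have sparser swabs and no stated infection rule, but the documents give no basis for putting a size on that effect.

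**What to change.** 1. **Definition.** In the SAP, define anti-N seroconversion from baseline at or before the day-56 visit, with a prespecified assay cut-off. Name the baseline sample, because SAP 5.7 and 6.1 define baseline differently.
2. **Use.** Either add seroconversion to PPS criterion 2, or run the primary ANCOVA with and without these subjects as a prespecified sensitivity analysis. The second is safer if anti-N sensitivity may differ by arm.
3. **Reporting.** Show exclusions by arm, separately for RT-PCR and anti-N.
4. **Consistency.** Reconcile criterion 2 with the PPS wording in Protocol 11.3.1 and with the booster-set rule in SAP 3.5.
5. **Long-term data.** Exclude or flag samples taken after a positive RT-PCR or anti-N seroconversion.

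This is a cheap improvement: SAP wording and an assay already planned, with no new visits or blood draws. It is not free. A cut-off must be justified, a few more subjects leave the PPS, infections just before day 56 may still go undetected, and sensitivity may vary by arm.

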9. STUDY SCHEDULE OF EVENTS AND PROCEDURES

9.1. Schedule of Events

In light of the public health emergency related to COVID-19, the continuity of clinical study conduct and oversight may require implementation of temporary or alternative mechanisms. Examples of such mechanisms may include, but are not limited to, any of the following: phone contact, virtual visits, telemedicine visits, online meetings, non-invasive remote monitoring devices, use of local clinic or laboratory locations, and home visits by skilled staff. Additionally, no waivers to deviate from protocol enrollment criteria due to COVID-19 will be granted. All temporary mechanisms utilized, and deviations from planned study procedures in response to COVID-19 are to be documented as being related to COVID-19 and will remain in effect only for the duration of the public health emergency.

Table 3: Schedule of Events for Arms 1, 2, 3, and 6a (Enrollment Wave 1) and Arms 7, 8, and 6c (Enrollment Wave 3)

Visit Period	Screening/Baseline				Vaccine Response Assessment				Follow-Up			Unscheduled Visit	ET		
Study Day	-21 to 1				15 ¹	29	43 ¹	57	71	183	267	380			
	Screening	Pre-dose	Dose ¹	Post-Dose											
Days After the First Vaccine Dose					14	28	42	56	71	168	252	365			
Window (day)					-1 to +3	±2	-1 to +3	±2	±2	±7	±14	±14			
Screening/Baseline and Key Laboratory Testing															
Inclusion/exclusion	X	X													
Informed consent	X														
Informed consent for optional FBR sub-study ²	X														
Informed consent for optional PGx sub-study ²	X														
Medical history	X														
Demographics	X														
Height and weight	X														
Pregnancy test (WOCBP) ³	X ³	X ³			X		X						X		
SARS-CoV-2 rapid (local/POC) RT-PCR ⁴	X ⁴	X ⁴			X ⁴	X ⁴	X ⁴	X ⁴	X ⁴	X ⁴	X ⁴	X ⁴	X ⁴		
SARS-CoV-2 rapid serology ⁵	X ⁵	X ⁵													
SARS-CoV-2 serology (central lab) ⁵	X ⁵													X	
Enrollment Wave and Treatment Assignment															
Site-managed assignment ⁶	X ⁶														
Randomization ⁶		X ⁶													
Study Drug and Vaccine Administration															
REGN10933+REGN10987 (arms 1, 2, 3, 7, and 8 only) ⁷			X ⁷												
Moderna mRNA-1273 vaccine (arms 1, 2, 3, 7, 8, 6a, and 6c) ⁷				X ⁷			X ⁷								
Biomarkers															
Serum for SARS-CoV-2 neutralization ⁸			X			X	X	X	X	X	X	X	X	X	
Serum for serology characterization ⁸	X				X	X	X	X	X	X	X	X	X	X	
Whole blood for PBMCs ⁸	X				X	X	X	X	X	X	X	X	X	X	
Serum for exploratory research	X				X	X	X	X	X	X	X	X	X	X	

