9.2.1.2. SARS-CoV-2 Rapid RT-PCR

At screening, the investigator or designee will verify that the subject has tested negative for SARS-CoV-2 by a rapid RT-PCR test. Historical test results will not be accepted.

Subjects will also be tested for SARS-CoV-2 infection by the rapid RT-PCR test using nasopharyngeal (NP) swabs throughout the study according to the respective Schedules of Events. Any post-baseline virology samples that test positive for SARS-CoV-2 will be banked for viral sequencing Section 9.2.3.4.

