3.5. Vaccine Booster Analysis Set

The vaccine booster analysis set includes Per Protocol Set subjects who signed the optional sub-study informed consent, have been vaccinated with the study-provided vaccine booster and did not have an adverse event of COVID (Preferred Terms of ‘COVID-19’, ‘Asymptomatic COVID-19’, ‘SARS-CoV-2 test positive’, ‘COVID-19 pneumonia’) or a positive PCR test prior to the post-booster follow-up sample collection.

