5.7.1. Analysis of Primary Vaccine Response Variable

The primary endpoint is the 50% inhibitory dilution (ID_{50}) neutralizing antibody titers of vaccine-induced neutralizing antibodies to SARS-CoV-2, assessed on 56 days after the first dose of the vaccine. The 56-day time point corresponds to study day 71 for study arms 1, 2, 3, 7, 8, 6a, and 6c, and study day 57 for study arms 4, 5, 9, 6b, and 6d. For all analyses, the vaccine alone arms (i.e. arms 6a, 6b, 6c and 6d) will be pooled in the analysis.

An analysis of covariance (ANCOVA) model with treatment group as a fixed effect and age as a continuous covariate will be run in order to perform the primary analysis for the PPS. The least squares mean estimates and associated 95% confidence interval for the endpoint will be reported for each treatment group, as well as for the relative differences between each combination of Moderna mRNA-1273 vaccine and REGN10933+REGN10987 arm (i.e. arms 1 - 5, and 7 - 9) and the pooled vaccine alone group.

Data may be fitted in the log 2 scale, and final outputs of geometric means and relative differences of the geometric mean ratio will be reported through the back-transformation.

Let $\hat{\mu}_A$, $\hat{\mu}_B$ denote the least squares mean estimates and $\hat{\sigma}_A^2$, $\hat{\sigma}_B^2$, $\hat{\sigma}_{AB}$ denote the associated estimated variances and covariance for the endpoint of interest of treatment groups A and B, respectively.

Geometric means and associated 95% confidence intervals for treatment groups A and B will be calculated as:

$$2^{\hat{\mu}_A}, (2^{\hat{\mu}_A - t_{df,\alpha} \times \hat{\sigma}_A}, 2^{\hat{\mu}_A + t_{df,\alpha} \times \hat{\sigma}_A}),$$

and

$$2^{\hat{\mu}_B}, (2^{\hat{\mu}_B - t_{df,\alpha} \times \hat{\sigma}_B}, 2^{\hat{\mu}_B + t_{df,\alpha} \times \hat{\sigma}_B}).$$

Relative difference of the geometric mean ratio and associated 95% confidence interval for treatment groups A and B will be calculated as:

$$(2^{\widehat{\mu}_A - \widehat{\mu}_B} - 1) \times 100\%, \left(2^{\frac{(\widehat{\mu}_A - \widehat{\mu}_B) - t_{df, \alpha} \times \sqrt{\widehat{\sigma}_A^2 - 2\widehat{\sigma}_{AB} + \widehat{\sigma}_B^2}}{2} - 1} \right) \times 100\%, \left(2^{\frac{(\widehat{\mu}_A - \widehat{\mu}_B) + t_{df, \alpha} \times \sqrt{\widehat{\sigma}_A^2 - 2\widehat{\sigma}_{AB} + \widehat{\sigma}_B^2}}{2} - 1} \right) \times 100\%.$$

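### PPS criterion 2 stops short of the day-56 visit, so a subject first RT-PCR positive on the swab taken with the primary serum stays in the primary analysis

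*SAP*

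**What the plan says.** **Primary set.** SAP 3.1 states: "The PPS is the primary analysis set for assessing vaccine response related endpoints". Its criterion 2 excludes subjects with a positive RT-PCR "diagnostic test result for SARS-CoV-2 infection at any time point prior to the scheduled visit 56 days after the first dose of vaccine".

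**Protocol version of the rule.** Protocol 11.3.1 excludes subjects who "Receive a positive diagnostic test result for SARS-CoV-2 infection before 56 days after the first dose of the vaccine". It leaves the finalized list of exclusions to the SAP.

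**Timing of the endpoint.** SAP 5.7.1: "The 56-day time point corresponds to study day 71 for study arms 1, 2, 3, 7, 8, 6a, and 6c"; for the remaining arms it is study day 57.

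**What happens at that visit.** In Protocol 9.1, Tables 3 to 5, the row "SARS-CoV-2 rapid (local/POC) RT-PCR" is marked at every visit of the vaccine response period, including this one. The row "Serum for SARS-CoV-2 neutralization" (Table 3, with equivalents in Tables 4 and 5) supplies the primary titre there. Protocol 9.2.1.2 confirms testing "using nasopharyngeal (NP) swabs throughout the study according to the respective Schedules of Events".

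**Infected subjects.** Protocol 6.1.2 keeps them on their visit schedule. It also asks for a swab as soon as possible after symptoms or an outside positive, at an unscheduled or a planned visit, whichever comes first.

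**Booster set.** SAP 3.5 excludes subjects with certain COVID adverse event terms "or a positive PCR test prior to the post-booster follow-up sample collection".

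**The concern.** The infection exclusion is there so that the titre measures vaccination and not infection. Protocol 3.2.1.2 and SAP 1.1 both say that exposure to the virus during the study would confound interpretation. A positive swab at the day-56 visit shows that the subject was already infected when the serum was drawn, or very close to it. As written, criterion 2 ignores that result because it is obtained at the visit and not before it. If the infection has already raised the titre, the mean of that subject's group is inflated. In a combination arm this would hide interference. In the vaccine-only group it would exaggerate it.

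**Working it through.** **1. Does any other rule remove the subject?** Take a subject whose first positive is the swab at the day-56 visit.

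| Rule | Effect on this subject |
|---|---|
| SAP 3.1 criterion 1 | None: concerns serology before the first vaccine dose |
| SAP 3.1 criterion 2 | None: the positive is at the visit, not before it |
| SAP 3.1 criteria 3 to 7 | None: concern other antibodies, vaccines, immunosuppression, blood products and incomplete dosing |
| SAP 3.1 criterion 8 | None: concerns the baseline titre |
| SAP 5.7 and 6.2 (data handling) | None: no titre is set aside for infection |
| SAP 3.2 (mFAS) | None: no post-baseline infection exclusion |
| SAP 5.7.5 (supplementary and subgroup) | None: covers waves, age and sex only |

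The subject enters the primary ANCOVA.

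**2. How old can such an infection be?** The preceding scheduled swab is at 42 days after the first dose (study day 57 or 43). The nominal gap is 71 − 57 = 14 days, or 57 − 43 = 14 days. With ±2 days at each end it is 14 − 4 = 10 to 14 + 4 = 18 days.

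**3. Do the two documents draw the same line?** No. The protocol counts days; the SAP refers to the visit, which has a ±2-day window.

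| Swab positive at a day-56 visit actually held on | Protocol 11.3.1 | SAP 3.1 |
|---|---|---|
| Day 54 or 55 after first dose | Excluded | Kept |
| Day 56, 57 or 58 | Kept | Kept |

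The SAP's reference to a scheduled visit could also mean the planned date or the date attended.

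**4. The plan's own precision figure.** Inputs from SAP 2.2: SD 0.30 log10, 30 per combination arm, 46 pooled controls. The ANCOVA has 9 group means and one age slope, so df = 286 − 10 = 276 and t = 1.969.

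Half-width = 1.969 × 0.30 × √(1/30 + 1/46) = 0.139, which rounds to the stated 0.14.

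**5. Size of the shift.** Shift in a group mean = k × δ / n, where k is the number of affected subjects and δ their extra titre. The documents give neither, so k = 1 to 2 and δ = 0.3 to 1.0 log10 are assumptions.

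- Pooled controls, n = 46: 1 × 0.3/46 = 0.007 to 2 × 1.0/46 = 0.043 log10. The geometric mean ratio against control falls by 1.5% to 9.5%.
- One combination arm, n = 30: 1 × 0.3/30 = 0.010 to 2 × 1.0/30 = 0.067 log10. The ratio rises by 2.3% to 16.6%.

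All of these are below 0.14. As to frequency, if 0.1% to 2% of subjects (assumed) are first positive at this visit, 286 × 0.001 = 0.3 to 286 × 0.02 = 5.7 subjects are expected in the whole trial.

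**6. Cost in precision of closing the gap.** Removing one subject from an arm of 30 gives 1.969 × 0.30 × √(1/29 + 1/46) = 0.140. Removing two gives 0.142.

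**The case against.** The case for leaving the rule alone has four parts.

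- **The gap is narrow.** Positives from unscheduled or outside tests before the visit already exclude a subject (Protocol 6.1.2, SAP 4.6.5). This is right, and a reader who inferred that the whole last 14 days is unprotected would be wrong. The gap is not empty, though. Asymptomatic infection depends on the scheduled swab, and someone with symptoms shortly before the visit may properly be tested there first.
- **A very recent infection may not yet have changed the titre.** That could justify keeping such subjects, but neither document says so, and with a gap of about 14 days since the last scheduled swab recency cannot be assumed.
- **Criteria 3 and 5 to 7 use the same cut-off.** They concern treatments given, where a visit boundary is natural. A positive swab differs because it reveals an infection acquired earlier.
- **The effect is small.** No hypothesis test is planned, and the largest control shift above is under a third of the half-width. This stands, and it limits how much weight the point carries.

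Three stronger readings are tempting but unsupported.

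- **Bias in a known direction.** One might argue that the antibodies prevent infection, so retained cases fall mainly among controls. The 66.4% reduction in Protocol 3.3.1 is for 1200 mg SC in household contacts. Here all PPS subjects have had two vaccine doses, arms 7 and 8 receive 48 mg and 12 mg, and Protocol section 1 expects no activity against Omicron.
- **A shift as large as 1.0/8 = 0.125 log10.** That needs a single-wave control arm of 8, whereas SAP 5.7.1 pools the vaccine-only arms. SAP 5.7.5 is most naturally read as waves 1 and 2 together and waves 3 and 4 together, with 30 and 16 controls. One subject then moves the mean by 0.3/30 = 0.01 to 1.0/16 = 0.06.
- **The same fault in the booster set.** SAP 3.5 also excludes by adverse event terms, including those for asymptomatic infection and a positive SARS-CoV-2 test, and its cut-off is the sample collection. Whether a same-visit positive counts is unclear; it is not plainly ruled out.

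**Conclusion.** The point holds on the wording. A subject first RT-PCR positive at the day-56 visit stays in the primary PPS analysis, and nothing else in the plan removes that subject. The protocol and SAP boundaries also disagree for visits held on day 54 or 55. The SAP is the finalized rule, so the protocol's day count does not close the gap.

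The numerical effect is probably minor, and its size rests entirely on the assumed counts and titre rises. The direction is not established. The reason to act is that a detected infection, which the plan itself treats as confounding, is kept although the result is already in hand. For the booster set, only a clarification is warranted.

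**What to change.** - Reword SAP 3.1 criterion 2 so that a positive RT-PCR excludes *at any time up to and including the visit at which the day-56 sample is drawn*, and align Protocol 11.3.1 to the same boundary. This also settles planned against actual visit date.
- Report the primary analysis with and without subjects first positive at that visit. The Amendment 5 history records an interim analysis of waves 1 and 2, so the rule would be changing after data were seen, and showing both results makes the effect of the change visible.
- In SAP 3.5, state that a positive swab at the post-booster visit counts as an exclusion.

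The cost is a few words and one extra run on data already collected. It may mean one or two fewer PPS subjects, with the loss of precision shown above. The real downside is a primary-set rule changed after interim data, which is why both results should be reported.
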